### 9.3.5 Efficacy analysis (mITT Population)

In general, the need for rituximab rescue will be considered “treatment failure” for the analysis of efficacy endpoints except cumulative CS and composite GTI score.

The analyses for efficacy endpoints involving clinical assessment of CR during the blinded treatment period will be performed based on data collected during on-site visits (i.e., not including data collected from remote visits) as the primary analyses.

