**CS dose up-titration for worsening disease:**

- 1. Severe relapse/flare or worsening disease at any time, which, in the opinion of the Investigator, is potentially life threatening**

Commence conventional immunosuppressive therapy and discontinue rilzabrutinib/placebo.

- 2. Non life-threatening worsening of disease during taper of CS prior to confirmation of ECP**

During Screening or the treatment periods of the trial, where an initial induction of CDA has not been achieved and blistering continues without improvement, CS should be increased by 50 to 100% every 5 to 7 days until confirmation of ECP. After ECP is confirmed CS taper should commence. Rituximab therapy may not be used in this situation. Patients who have been treated with a minimum of 1.5 mg/kg/day of corticosteroids for 2 weeks and have not achieved control of disease activity may be eligible after discussion with Principia to receive rituximab. For patients who are unable to escalate CS up to 1.5 mg/kg/day due to documented AEs related to CS and cannot achieve CDA following 2 weeks of treatment with their maximally tolerated CS dose, rescue with rituximab therapy may be offered. Please consult with the Medical Monitor.

- 3. Non life-threatening worsening of disease during taper of CS after confirmation of ECP**

- Go back to last CS dose level if >3 lesions reappear during the tapering of oral corticosteroid therapy (where relapse/flare, as defined below, has not occurred)
- If a more severe full relapse/flare occurs (ie, the appearance of ≥3 new lesions within a month that do not heal spontaneously within 1 week, or there is extension of established

lesions), increase the CS dose by going back to the second to last dose until control of the lesions is achieved within 2 weeks, then resume taper

- If disease control is still not reached despite this, go back to initial dose or higher as necessary, and resume taper when ECP is confirmed again

It is recommended to follow the CS Guidelines during the Long Term Extension.

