### **Rituximab Management during Blinded Treatment Period**

Rituximab for second “qualifying relapse/flare”:

- “Qualifying relapse/flare” for this purpose is defined as a relapse/flare occurring after CDA is achieved, ECP has been confirmed and CS taper has begun, that is not life-threatening (when a patient should be withdrawn) but is severe enough such that the PDAI total activity score is equal to or greater than the Screening or Day 1 baseline PDAI score (whichever is higher) for that patient. For example, if the Screening PDAI was 25, the Day 1 baseline was 21, and the relapse/flare PDAI 23, the relapse/flare would not be severe enough to be “qualifying”. Whereas if the relapse/flare PDAI was  $\geq 25$  it would be “qualifying”.
- Where a second qualifying relapse/flare occurs meeting the above definition, and it is at or after the Week 5 Visit, then one course of rituximab, which consists of two intravenous doses of 1 gram two weeks apart, may be administered, unless contraindicated.
- Oral CS doses should be managed as indicated for the patient at the time of the 2nd qualifying relapse/flare
- Rituximab should be administered as recommended in the Pharmacy Manual.
- Patients should not be unblinded to treatment assignment and should continue in the trial.

[figure not shown]

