#### 6.1.5.1. Imputation Procedures for the Primary Efficacy Endpoint

For the primary efficacy endpoint (the proportion of patients who are in CR from Week 29 to Week 37 with a prednisone dose of  $\leq 10$  mg/day), patients with missing data due to study withdrawal will be considered as non-responders. A patient who received a rituximab dose prior to Week 37 will also be counted as a non-responder. [REDACTED]

[REDACTED]

- [REDACTED]
- [REDACTED]

[REDACTED]

[REDACTED]

[REDACTED]

[figure not shown]
[REDACTED]

[REDACTED]

Tipping point analyses (Yan, 2009) will be done to investigate the impact of missing data and lost to follow-up (LTF). The tipping point analysis will look at all possible combination of

converting missing data to a responder, starting at 0 and ending at all are responders. The cases where the statistical significance tips from significance to non-significance (defined as a two sided p-value  $>0.05$ ) will be listed. A complete list of all combinations will also be presented. If the imbalances that leads to a change in interpretation are clinically implausible then the results of the primary analysis will be deemed reliable

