#### **6.1.5.2. Imputation Procedures for Secondary Endpoints**

### Responder analyses:

If a patient received a rituximab dose prior to Week 37, the patient will be counted as a non-responder starting from the date of first dose of rituximab for following responder analyses:

- The proportion of patients who are in CR from Week 29 to Week 37 with a CS dose of  $\leq 5$  mg/day
- The proportion of patients who have a PDAI score  $< 3$  from Week 29 to Week 37 with a CS dose  $\leq 10$  mg/day

For the derivation of the following parameters:

- proportion of patients having three or more lesions within 1 month or extension of established lesions that do not heal within 1 week from Baseline to Week 37
- proportion of patients with at least one disease flare/relapse from initial control of disease activity (CDA) to Week 37,

A missing value will be considered as Yes with exception of the following:

- A 'No' can be inferred if adjacent visits are complete and reflect this same outcome. No more than one disease assessment can be imputed for this endpoint (i.e. this imputation is not applicable to consecutive missing visits). Note that, this imputation is not applicable at Week 37 when the study treatment a patient receives before and after the visit could be different.

If a patient received a rituximab dose prior to Week 37, the patient will be counted as Yes for the analyses of these two parameters.

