### Time to event analyses:

For the analyses of following parameters,

- Time to first CR with a CS dose  $\leq 10$  mg/day CS, from Baseline to Week 37
- Time to first CR with a CS dose  $\leq 10$ mg/day, from Baseline to Week 61
- Time to initial flare/relapse from initial CDA to Week 37.

If a patient receives a rituximab therapy, the study data will be censored at the date of first rituximab administration for the above time to event analyses.

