**Table 4: Event and Censoring Details for Time to First CR with a CS dose at or below 10 mg/day**

Situation	Date of First CR/ Date of Censoring	Censored/ Event
No post baseline assessments	Date of first dose	Censored
Patient in CR status and with a CS dose of $\leq 10$ mg/day	First date that patient is in CR status and with a CS dose of $\leq 10$ mg/day as identified in Section 6.1.9.	Event
Rituximab administered	Date of first Rituximab administration	Censored
No CR with a CS dose of $\leq 10$ mg/day during the Blinded Treatment Period	Date of last efficacy assessment during blinded treatment phase (through Week 37)	Censored
Study discontinuation	Date of last efficacy assessment prior to or on the date of treatment discontinuation	Censored
Death before CR	Date of death	Censored

Note: Patients will be censored prior to a CR event at the earliest date of the censored events above should a censoring reason occur. Censoring reasons may be categorized for reporting (eg, by discontinuation reason).

- Three or more lesions within 1 month that do not heal spontaneously within 1 week or extension of established lesions = Yes if any of the following conditions are satisfied:
  - eCRF entry “Have new lesions appeared within a month that did not heal spontaneously within 1 week? OR Have there been extension of established lesions?” = Yes for any visits from Baseline up to Week 37.
  - At this visit, Has a Relapse occurred or is continuing?

The number of instances with investigator assessments of disease worsening will also be derived and categorized for reporting as 0, 1, 2, and  $\geq 3$ . After the first worsening, a patient can have additional worsening, but only after the patient returns to CDA first, and then the next worsening can happen.

- PDAI score  $< 3$  from Week 29 to Week 37 with a CS dose of  $\leq 10$  mg/day = Yes if the following conditions are both satisfied:
  - PDAI  $< 3$  = Yes for all visits from Week 29 through Week 37
  - Daily prednisone dose is  $\leq 10$  mg/day from Week 29 through Week 37 as defined in Section 6.1.9.
  - No Rituximab therapy prior to Week 37.

After applying the CS dose imputation as described in Section 6.1.5.2, a patient with partial missing data (missing PDAI assessment or CS dose) or complete missing data at any scheduled visit will be considered as a non-responder.

- Change from baseline = value at current time point – value at Baseline.

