## 8.2. Key Secondary Efficacy Analyses

The key secondary endpoint of Cumulative CS dose from baseline to Week 37, adjusted for time to study discontinuation will be calculated using the summation of the CS data as described in Section 6.1.9 and will be analyzed using an ANCOVA model with terms for treatment group and disease history. The estimated mean difference in cumulative CS usage (PRN1008 minus

placebo) and the associated 95% CI will be reported. Missing data for this endpoint is described in Section 6.1.5.2. The “time to study discontinuation” covariate is up to study discontinuation, first Rituximab administration if any, or the end of the blinded treatment period whichever happens first.

If outliers or skewed data is present, sensitivity analysis will be conducted on this secondary endpoint of average weekly CS usage over 36 weeks in which the data will be rank-transformed prior to analysis.

Cumulative CS dose from Week 37 to Week 61 will be analyzed similarly.

Cumulative duration of CR with CS dose  $\leq 10$ mg/day from Baseline to Week 37, will be based on a zero-inflated negative binomial model with terms for treatment group and disease history. The p-value and estimated treatment difference (parameter difference of PRN1008 minus placebo) from the negative binomial component will be reported, along with the 95% CI for the estimated parameter. The difference estimate will also be back-transformed (e.g. exponentiated) to demonstrate the relative difference in the number of pemphigus free days between treatment groups. Cumulative duration of CR with CS dose  $\leq 10$ mg/day from Baseline to Week 37 will also be summarized based on descriptive statistics.

A Kaplan Meier analysis will be used to estimate the median and other quartiles for Time (Days) to first CR with a dose of  $\leq 10$  mg/day, along with two-sided 95% confidence intervals. The number of events and censored observations will be presented as well as graphical representations of estimated survival curves. A hazard ratio for treatment comparisons will be presented, along with its 95% confidence interval, based on a Cox regression model with terms for treatment group and disease history. The endpoint will be evaluated based on a p-value from a log-rank test stratified by disease history for treatment group comparison. In addition, a landmark analysis will be done at Week 37 in the key secondary analysis and at Week 61 for the other secondary analysis.

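### Time to first CR, an alpha-controlled key secondary endpoint, is censored at rituximab rescue, although the protocol's general rule and the SAP's other response endpoints count rescue as failure

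*SAP*

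**What the plan says.** - **Protocol 9.3.5** states, as a general rule, that the need for rituximab rescue is treatment failure "for the analysis of efficacy endpoints except cumulative CS and composite GTI score". Time to first CR is not among the exceptions.
- **SAP 6.1.5.1**, primary endpoint: "A patient who received a rituximab dose prior to Week 37 will also be counted as a non-responder".
- **SAP 6.1.5.2**, CR and PDAI responder endpoints: "the patient will be counted as a non-responder starting from the date of first dose of rituximab for following responder analyses". The ABQOL-zero endpoint is handled the same way.
- **SAP 6.1.5.2**, time to first CR (to Week 37 and to Week 61): "the study data will be censored at the date of first rituximab administration for the above time to event analyses". Table 4 in SAP 6.1.8 lists rituximab as a censoring reason and adds: "Patients will be censored prior to a CR event at the earliest date of the censored events above should a censoring reason occur".
- **SAP 8.2** tests the endpoint with a log-rank test stratified by disease history and says that "a landmark analysis will be done at Week 37 in the key secondary analysis". It does not define the landmark method. The readable text plans no analysis of this endpoint with rescue as failure.
- **Protocol Appendix 1** gives two routes to rescue in the blinded period. One is a second qualifying flare, meaning one "severe enough such that the PDAI total activity score is equal to or greater than the Screening or Day 1 baseline PDAI score", whichever of the two is higher. The other is for patients who have had at least 1.5 mg/kg/day "of corticosteroids for 2 weeks and have not achieved control of disease activity may be eligible", with a similar provision for patients who cannot tolerate that dose.
- **SAP Section 10** declares no change from the planned analysis.

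**The concern.** The same event is read in two ways. A patient rescued before any CR on low-dose CS is a failure for the primary endpoint, but for time to first CR that patient leaves the risk set as if merely unobserved from then on.

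Kaplan-Meier and log-rank methods assume that a censored patient would have gone on to CR at the same rate as those still at risk. Patients rescued because their disease flared back to baseline severity, or never came under control, are unlikely to meet that assumption.

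The endpoint carries alpha. Under SAP 6.1.4 it is tested third among the key secondaries in PV patients and again in the whole mITT population, and testing stops at the first non-significant result. A distorted result in PV patients would therefore also decide whether any of the three whole-population key secondary tests is formally made.

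**Working it through.** The plan states no rescue rate, no CR rate for this endpoint and no power for it, so there is no figure to reproduce. The inconsistency rests on the text. The arithmetic below shows only direction and possible size, and every rate in it is an assumption.

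**1. Direction by hand.** Let p be the share reaching CR by Week 37 and r the share rescued before CR who would not otherwise reach it. With rescue as failure the CR estimate is p. With censoring it rises towards p/(1 − r), the limit reached if all rescue came before the first CR.
- p = 0.30, r = 0.25: limit 0.30/0.75 = 0.40
- p = 0.50, r = 0.05: limit 0.50/0.95 = 0.526
- r = 0.05 in both arms: 0.526 − 0.316 = 0.211, against a true difference of 0.200

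So the arm with more rescue gains more, and equal rescue slightly widens the gap.

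**2. Simulation A.** 60 per arm (120 randomised 1:1), 3,000 runs, unstratified log-rank at two-sided 0.05, CR at scheduled visits from Day 85 to Day 253, rescue between Days 57 and 224, rescued patients not otherwise reaching CR. Pairs are active/placebo.

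| True CR | Rescued before CR | KM CR, censored | KM CR, held at risk | Rejection, censored | Rejection, held |
|---|---|---|---|---|---|
| 50/30% | 5/5% | 52.0/30.9% | 50.0/29.8% | 0.62 | 0.61 |
| 50/30% | 5/15% | 52.1/33.8% | 50.1/30.2% | 0.49 | 0.60 |
| 50/30% | 5/25% | 52.1/37.0% | 50.1/30.1% | 0.36 | 0.60 |
| 50/30% | 15/5% | 56.9/31.2% | 50.1/30.1% | 0.76 | 0.60 |
| 35/35% | 5/5% | 36.3/36.1% | 35.0/34.8% | 0.055 | 0.053 |
| 35/35% | 5/25% | 36.3/43.4% | 35.0/35.1% | 0.107 | 0.047 |
| 35/35% | 25/5% | 43.5/36.4% | 35.2/35.1% | 0.107 | 0.053 |

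With no true difference, the excess rejections fall almost wholly against active in the sixth row and in favour of active in the seventh (0.104 of 0.107 in each).

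**3. Simulation B, milder assumptions.** 45 per arm (half the target minimum of 90 PV patients), log-rank stratified by disease history, 50% of never-rescued placebo patients in CR by Week 37, hazard ratio 1.8, rescue between Days 90 and 200, 20% of rescued patients in CR first, 10% dropout.

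| Rescued, active/placebo | Mean Z, censored | Mean Z, held at risk |
|---|---|---|
| 2/5% | 2.10 | 2.14 |
| 5/10% | 2.07 | 2.12 |
| 8/20% | 2.08 | 2.23 |
| 12/12% | 1.90 | 1.81 |
| 20/8% | 1.66 | 1.32 |

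Here the break-even lies where placebo rescue is about 1.4 to 1.5 times active rescue. The two simulations agree on direction and differ in size, because A assumes larger imbalances and no CR at all in rescued patients.

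**The case against.** A reader might infer that the SAP flatly contradicts the protocol. The documents do not support that:
- Protocol 9.3.5 states a general rule, which admits exceptions, and does not say what failure means for a time-to-event endpoint.
- It leaves further detail on the key secondaries to the SAP. The synopsis makes the SAP the final authority, and protocol Section 9 lets it modify the plan and says that major modifications will be reflected in the study report.
- The SAP states its rule twice and clearly, so an analyst knows what to run.
- The SAP change log covers only changes since Version 1, so its silence proves little.

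All of that stands. It makes a different rule permissible; it does not give a reason for one. The synopsis also asks the SAP to attend to changes of substance from the protocol, and Section 10 declares none. Version lag is not the explanation: the SAP cites amendment 6, and the amendment history shows the failure rule being moved into 9.3.5 at that amendment.

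Three further objections have some force. Table 4 also censors discontinuation and death, which may be outcome-related too. Rescue differs in that the protocol has an explicit general rule for it and rescued patients stay on trial. The flare route is narrow: it needs confirmed ECP, a started taper and two qualifying flares. The no-control route is separate, and its patients will seldom have had a CR first. Finally, parts of SAP 6.1.5 cannot be read, so an unseen supportive analysis cannot be ruled out, but the passages that set this rule are legible.

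**Conclusion.** The point holds for one endpoint. Time to first CR is censored at an outcome-driven event that the protocol generally, and the SAP for its primary and responder endpoints, treat as failure. The censoring overstates the Kaplan-Meier CR rate. It distorts the comparison against rilzabrutinib if placebo has clearly more rescue, and in its favour if rilzabrutinib has more. At low, equal rescue the effect is small. Only patients rescued before a first CR matter, and the primary endpoint is untouched. The size is unknown: it rests wholly on assumed rescue and CR rates, and ranges from negligible to a power change from 0.60 to 0.36.

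Two stronger readings should be resisted. One is that the rule inflates the result for rilzabrutinib. If the drug works, more rescue on placebo is the likelier pattern, and that works against it. The other is that the cut-off at rescue is equally wrong for the remaining endpoints. Cumulative CS and GTI are exempt under protocol 9.3.5, and their handling after rescue is a choice of estimand. Flare count, PDAI, ABQOL, EQ-5D-5L and time to flare lie outside the testing hierarchy. For time to flare the practical effect is also slight, since the flare route requires earlier flares and patients who never reach disease control are not in that analysis.

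**What to change.** Before unblinding:
1. In SAP 6.1.5.2 and Table 4, keep patients rescued before CR in the risk set as non-events to the end of the blinded period (Day 253, the Week 37 target day), and do not count a CR reached after rescue. Apply this to the Kaplan-Meier, log-rank and Cox analyses.
2. Use the same rule for the Week 37 landmark and, to Day 421, for the Week 61 version.
3. Keep censoring at rescue as a sensitivity analysis.
4. If the sponsor prefers censoring as the main analysis, declare and justify it in SAP Section 10 and add the rescue-as-non-event analysis beside it.

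The cost is a few lines of SAP text and a little extra programming, with no new data, since rescue dates and CR assessments are already collected. No change to cumulative CS, GTI or the endpoints outside the hierarchy is needed. At most, a supportive cumulative CS analysis over the full 36 weeks could be added.

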### Cumulative CS dose:

- Cumulative CS dose from Baseline to Week 37

If a patient receives a rituximab therapy, the CS dose up to the date of the first dose of rituximab (including CS dose on the date of the first dose of rituximab) will be included in the analyses.

### Other analyses:

For analyses of following parameter,

- Change in PDAI score from baseline to Weeks 5, 13, 25, 37 and 61
- Total number of disease flares/relapses from initial CDA to Week 37
- Glucocorticoid Toxicity Index (GTI) score at Week 37
- Change in Autoimmune Bullous Disease Quality of Life (ABQOL) score from baseline to Weeks 5, 13, 25, 37, and 61

- Change in EuroQOL-5 Dimension 5 Level (EQ-5D-5L) results (visual analog scale [VAS] results and individual dimension) scores from Baseline to Weeks 5, 13, 25, 37 and 61.

If a patient receives a rituximab therapy, the study data up to the date of the first dose of rituximab (but not including data from the date of the first dose of rituximab) will be included in the analyses.

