CS taper should not begin until ECP has been achieved.

If the first documentation of CDA coincides with no disease activity (PDAI = 0), a follow-up visit  $\geq 2$  weeks later must still confirm that no new lesions are seen and PDAI = 0. At this time the patient is deemed to have confirmed CDA, ECP, and CR and therefore CS tapering can begin. If new lesion(s) are seen, the patient is no longer in CDA and therefore CS tapering should not begin. If a patient has not achieved CDA or new lesions emerge or existing lesions worsen but do not meet definition of relapse/flare, refer to Appendix 1 [Section 12.1](#) regarding increasing steroid dosage.

Throughout the Blinded Treatment Period, patients who fail to respond to treatment or experience a worsening of disease should have their CS dose increased per CS Management Guidelines (Appendix 1 [Section 12.1](#)) until CDA is obtained. If ECP is not achieved in a timely manner, it is encouraged that CS dose be further increased unless clinically contraindicated. The Principal Investigator (PI) should consult with the Medical Monitor in such cases.

Efficacy Outcome Assessment should be performed per the Efficacy Outcome Assessment Flowchart, Appendix 8 [Section 12.8](#).

Once patients achieve CR on a dose of 5 mg/day of CS, that dose should be maintained (not tapered further) until Study Week 37 (time of primary endpoint).

Rituximab treatment may be administered during the Blinded Treatment Period at or after the Week 5 Visit, only after a second “qualifying relapse/flare” occurs, unless contraindicated (Appendix 1 [Section 12.1](#)).

If rituximab is administered, patients should continue to take rilzabrutinib/placebo, remain on trial and blinded to treatment assignment. After completing the Blinded Treatment Period, patients will enter the Open-Label Extension Period to receive active treatment with rilzabrutinib described below. A patient in the Blinded Treatment Period requiring an additional “top up” dose of rituximab after their initial rituximab course of treatment must be discontinued from the trial.

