#### 6.1.10. GTI Scores

The Glucocorticoid Toxicity Index is a proprietary licensed instrument from Massachusetts General Hospital (Miloslavsky 2017). It was developed to assess glucocorticoid (GC)-related morbidity and GC-sparing ability of other therapies.

The GTI is composed of two components, the Composite GTI and the Specific List. The Composite GTI consists of nine domains (body mass index (BMI), glucose tolerance, blood pressure, lipid, bone mineral density, glucocorticoid-induced myopathy, skin toxicity, Neuropsychiatric toxicity, and infection) on common steroid-related adverse events anticipated to occur in  $\geq 5\%$  of patients treated in a clinical trial involving glucocorticoids. Note that for this study bone mineral density was not collected, and therefore not included in the derivation. The Specific List consists of 23 items (11 domains) that are mainly less common but serious adverse effects, serving as a complementary tool to the Composite GTI to ensure that all important elements of glucocorticoid toxicity were captured.

The domains of the Composite GTI and the specific list of the GTI will be assessed at Day 1, Week 13, Week 25, Week 37. The details on the derivations of baseline glucocorticoid toxicity score are provided in Appendix 2.

**Domain-specific score** for each patient at a visit is defined as the weight assigned based on the change in severity level as described for each domain in Appendix 3.

**Composite GTI score** for each patient at a visit is the sum of 8 domain-specific scores at each visit.

**Cumulative GTI score** is the sum of composite GTI score across visits. Two cumulative GTI scores, CWS and AIS, will be defined.

- **Cumulative worsening score (CWS)**

CWS is designed to assess cumulative GC toxicity, regardless of whether the toxicity has lasting effects or is transient. New toxicities that occur are added, but toxicities that

appear to resolve on follow-up are not removed. Thus, the CWS serves as a lasting record of GC toxicity observed and can only increase or remain the same over time.

CWS will be lower in the treatment arm compared to the placebo arm at the end of trial, if the treatment is effective at decreasing GC toxicity over time.

- **Aggregate improvement score (AIS)**

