- b) For improvement score, only the most severe infection occurring among Week 13, Week 25, and Week 37 is scored.

**Step 2:** Calculate composite worsening score and improvement score at each visit by summing the 8 domain-specific score.

- a) For composite worsening score, sum the 8 domain-specific worsening scores.
- b) For composite improvement score, sum the 8 domain-specific improvement scores.

**Step 3:** Calculate cumulative GTI scores by summing composite scores across visits.

- a) For CWS at Week 37, summing composite GTI worsening score at Week 13, Week 25 and Week 37.
- b) For AIS at Week 37, summing composite GTI improvement score at Week 13, Week 25 and Week 37.

The detailed information for the derivation of Glucocorticoid Toxicity Index are presented in Appendix 3.

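### SAP 6.1.5.2 cuts GTI data at first rituximab although protocol 9.3.5 exempts composite GTI from the rescue rule; the departure is undeclared and the Week 37 steroid-toxicity comparison becomes conditional on rescue

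*SAP*

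**What the plan says.** **Protocol.** Section 9.3.5 sets a general rule that rituximab rescue is treatment failure "for the analysis of efficacy endpoints except cumulative CS and composite GTI score". The synopsis (section 1.1) and section 4.1 say that after rituximab "patients should continue to take rilzabrutinib/placebo, remain on trial and blinded to treatment assignment". Table 2 schedules a GTI assessment at Week 37, so that assessment is due for a rescued patient who remains on trial.

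**SAP rule for rescued patients.** Section 6.1.5.2, under Other analyses, lists "Glucocorticoid Toxicity Index (GTI) score at Week 37" together with PDAI change, flare count, ABQOL and EQ-5D-5L. After rituximab, the analysis of every item on that list includes only "the study data up to the date of the first dose of rituximab (but not including data from the date"; everything recorded on or after that day is dropped.

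**SAP derivation and test.** Section 6.1.10 says the GTI domains "will be assessed at Day 1, Week 13, Week 25, Week 37". Step 3 defines the two cumulative scores, the cumulative worsening score (CWS) and the aggregate improvement score (AIS): "For CWS at Week 37, summing composite GTI worsening score at Week 13, Week 25 and Week 37" and "For AIS at Week 37, summing composite GTI improvement score at Week 13, Week 25 and Week 37". Table 6 and section 8.3 test both at Week 37 by ANCOVA, with treatment and disease history as fixed effects and baseline GTI score and baseline CS dose as covariates.

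**Declared changes.** SAP Table 1 has no entry on GTI after rescue, and section 10 records changes from the planned analysis as not applicable.

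**The concern.** The protocol singles out GTI as an endpoint that rescue should not turn into a failure. The SAP gives it the same cut as endpoints with no such exemption.

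Reducing the adverse effects of CS is a stated efficacy objective. By Appendix 1 of the protocol, rescue follows a second flare with PDAI at or above its pre-treatment level, or failure to gain disease control after two weeks at high or maximally tolerated CS doses. Such patients plausibly carry more steroid toxicity than others. Receiving rituximab is also a post-randomisation event that an effective drug would make less frequent.

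Removing or shortening these patients' GTI records means the arms are no longer compared as randomised. Any part of the toxicity benefit that comes from avoiding treatment failure is lost from the estimate.

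**Working it through.** No figure in the plan depends on this point, so there is nothing to reproduce. The check follows a rescued patient through the SAP and then illustrates the size.

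**Step 1: what survives the cut.** Appendix 1 allows rituximab for a second qualifying flare at or after Week 5. Post-baseline GTI visits are Weeks 13, 25 and 37.

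- First dose before the Week 13 GTI: no post-baseline composite is kept.
- First dose between the Week 13 and Week 25 GTI: only Week 13 is kept.
- First dose between the Week 25 and Week 37 GTI: Weeks 13 and 25 are kept.

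The Week 37 composite is discarded in every case.

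**Step 2: what happens to CWS and AIS.** Each is a sum of three composites, and at least one is now absent. The readable SAP text gives no partial-sum, carry-forward or imputation rule for GTI. Section 6.1.5 promises imputation under criteria in that section, but section 6.1.5.1 is partly redacted and Appendices 2 and 3, which hold the GTI derivation detail, are not in the supplied text. Two outcomes are possible:

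- *No partial sum.* The Week 37 score is missing, and a single-time-point ANCOVA drops the patient.
- *Partial sum allowed.* The patient stays in without post-rescue toxicity. For CWS, negative domain scores are set to 0, so a partial sum can never exceed the full sum; the arm with more rescue has its mean lowered more. For AIS the direction is not fixed, because composites can be negative.

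The protocol's own model for GTI (section 9.3.6, other secondary: a repeated-measures model of change to each visit) would at least have kept visits before rescue.

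**Step 3: size under full exclusion.** The documents give about 60 patients per arm (protocol 4.1). They give no rescue rate and no GTI SD, so the remaining inputs are assumptions: rescue proportions r0 (placebo) and r1 (active); rescued patients D = 0.5 to 1.0 SD worse in both arms; non-rescued patients alike in both arms.

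- All-data difference (active minus placebo) = (r1 − r0) × D
- Difference after exclusion = 0
- Patients lost = 60 × r0 + 60 × r1

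| Rescue, placebo v active | Patients lost | Analysed, placebo v active | All-data difference, D = 0.5 | D = 1.0 |
|---|---|---|---|---|
| 5% v 5% | 3 + 3 = 6 | 57 v 57 | 0 | 0 |
| 10% v 5% | 6 + 3 = 9 | 54 v 57 | −0.05 × 0.5 = −0.025 SD | −0.05 SD |
| 20% v 5% | 12 + 3 = 15 | 48 v 57 | −0.15 × 0.5 = −0.075 SD | −0.15 SD |
| 30% v 10% | 18 + 6 = 24 | 42 v 54 | −0.20 × 0.5 = −0.10 SD | −0.20 SD |

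In each row the last two columns are the amount that the cut removes from the estimate.

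**The case against.** **The conflict is softer than outright contradiction.** The protocol rule is introduced as a general one and lifts only the failure label. It does not say in words that GTI collected after rituximab will be analysed. The SAP does not score rescued patients as GTI failures; it truncates them, and section 6.1.5.2 also truncates cumulative CS, the other exempt endpoint. The synopsis makes the SAP the final authority. This stands in part. A reader might infer that the protocol mandates use of post-rituximab GTI. The text does not go that far, though it is the natural reading, because GTI is not a responder endpoint and an exemption from failure scoring otherwise does little. The synopsis sentence that gives the SAP authority also says the SAP will attend to substantive changes from the protocol, and this one goes unmentioned. Amendment 07 revised section 9.3.5 and kept the exemption.

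**Complete exclusion is not proven.** A reader might infer that rescued patients have no Week 37 score at all. That depends on appendices that cannot be seen, so only the either/or conclusion in the working is supported.

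**The size is guesswork.** This stands. A reader might be tempted to quote a loss of power. Without an SD, a mean or a rescue rate in the documents, no power figure can be supported, and at low or equal rescue rates the effect is small or nil.

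**Truncation can be a defensible choice.** GTI has an infection domain, and the protocol describes the combination with rituximab as more intensive immunosuppression, so later scores may mix rescue effects with steroid toxicity. This is a reason to keep the truncated analysis as supportive and to state which question each analysis answers. It does not justify leaving the departure undeclared.

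**GTI is not the only view of steroid harm.** CS-related adverse events are tabulated in the whole Safety Population with no stated rituximab cut (SAP 9.1.1), so rescued patients' toxicity is not hidden from the report.

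**Conclusion.** The point holds as an undeclared departure from the protocol's exemption and as a selection problem in the Week 37 GTI comparison. Whether rescued patients drop out or contribute shortened scores, the result is conditioned on an event after randomisation that treatment can affect. If rescue is more frequent on placebo and rescued patients have more steroid toxicity, the between-arm difference is understated.

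The size is unknown. On the assumptions in the table it runs from nil, through 0.025 to 0.05 SD at 10% v 5% rescue, to about 0.2 SD at 30% v 10%. The nil result at equal rates also requires the excess toxicity of rescued patients to be equal in the two arms.

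A reader might infer a threat to the trial's main conclusions. The documents do not support that. GTI is an other secondary endpoint outside the hierarchy in SAP 6.1.4, and the GTI rule leaves the primary and key secondary tests unaffected.

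**What to change.** - Remove the Week 37 GTI score from the list under Other analyses in SAP 6.1.5.2.
- State that the main GTI analysis (domain, composite, CWS and AIS) uses all GTI data collected through Week 37 regardless of rituximab. Keep the rituximab-truncated version as supportive.
- State the rule for a missing GTI visit, including whether a partial sum is allowed for CWS and AIS.
- Reconcile the parallel cut of cumulative CS at first rituximab in SAP 6.1.5.2 with protocol 9.3.5, or declare it as a change in SAP section 10.
- If the sponsor prefers to keep the GTI cut as the main analysis, declare it in section 10 with the question it answers and its missing-data rule.

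The cost is a few lines of SAP wording and one supportive table. No new data collection is needed, because the Week 37 GTI is already scheduled for rescued patients who stay on trial.
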